## Study Synopsis:

Anhedonia and abnormalities in reward behavior are core features of overweight/obesity (OW), a highly prevalent condition within MDD populations and is independently associated with reward disturbances. We therefore aimed to investigate the brain substrates subserving reward and motivation in adults with overweight/obesity. Herein, we are primarily interested in three overlapping, yet distinct aspects, of anhedonia. We are primarily interested in motivation, reward valuation, and reward learning towards addressing the measurement of each of these respective subdomains, eligible participants will complete validated gold standard measures (i.e. the Effort Expenditure for Rewards Task (EEfRT) (reward valuation), Probabilistic Reward Task (PRT) (reward learning), and the Monetary Incentive Delay (MID) task (reward anticipation)).

Twenty adults with overweight/obesity will complete all tasks at a single visit with two of the tasks being completed prior to MRI and one of the tasks (i.e. EEfRT) will be completed during MRI acquisition.

The **primary aim** of this pilot study is to determine whether associations exist between obesity and decreased performance on the respective motivation/reward paradigms. In addition, associations between performance on reward tasks and functional connectivity, as measured by MRI and DTI, a secondary objective is to ascertain whether associations exist between performance on the motivation reward tasks and gold standard measures of food intake (i.e. food diary) and energy expenditure (i.e. calorimetry).

## Introduction

Anhedonia is a significant complaint and psychopathology in OW. Anhedonia is defined as markedly diminished interest or pleasure in all, or almost all, activities for an extended period of time. Anhedonia is a core criterion item for the diagnosis of MDD and OW, and is a robust predictor of poor longitudinal course of symptoms. Existing psychological and pharmacological treatments are relatively ineffective for treating anhedonia, as they have little effect, and in some cases may even worsen anhedonic symptoms. As a result, anhedonia is one of the most prevalent residual symptoms following treatment with antidepressants in individuals with MDD and OW.

Anhedonia includes elements of multiple reward processes. Reward systems are primarily responsible for responses to positive motivational situations or contexts, such as reward seeking, and reward/habit learning. Evidence indicates that individuals with mood disorders exhibit abnormalities in multiple subcomponents of reward. One of the main reward sub-constructs of interest in MDD is reward valuation, which includes the measurement of value and/or incentive salience of a prospective outcome and the willingness to work for it (i.e. effort). A consistent finding in MDD has been a decrease in the willingness to expend effort for rewards. Individuals with depression display reduced motivation on effort-based decision making, a dissociation between liking a reward and the willingness to exert effort for it, and an increased subjective feeling of having exerted more effort.

Replicated evidence indicates that OW is highly prevalent in MDD populations. Meta-analytical studies have estimated the prevalence of obesity in MDD between 30 and 70%. Conversely, OW has been consistently associated with motivational deficits, to both food and non-food rewards. Evidence indicates that in obesity the anticipatory reward response seems to be increased, whereas, similar to MDD, the willingness to invest effort is diminished.

Within MDD populations, obesity, and its metabolic correlates (e.g. insulin resistance), have been associated with increased self-reported anhedonia. As a result, anhedonia has been proposed as a key clinical mediator between MDD and metabolic comorbidities.

Nevertheless, few studies have used objective methods to assess reward deficits in populations with MDD and obesity. Herein, we aim to explore the role of OW in effort-based decision making in overweight/obese adults with varying levels of body mass index (BMI) above 30kg/m^2. We primarily aim to investigate the effects of OW correlation with effort for rewards, as measured by the Effort Expenditure for Rewards Task (EEfRT). The secondary aim is to examine the associations between effort-based decision-making as measured by EEfRT, with MRI/DTI measured alterations in reciprocity between reward and cognitive control circuits.

We **hypothesize** that obesity is associated with deficits in each of the reward paradigms we have selected. We also **hypothesize** that the foregoing disturbances correlate with functional disconnectivity within reward/cognitive control networks.

## Methodology

### Participants

Participants will be identified at the Brain and Cognition Discovery Foundation (BCDF). Twenty subjects with obesity, will be enrolled. All patients will be assessed for concurrent psychiatric disorders (e.g. mood disorders). Eligibility criteria are as follows: inclusion criteria: (a) 18-65 years of age; (b) meeting DSM-V criteria for: (i) major depressive disorder (symptomatic or asymptomatic in any phase of the illness) or (ii) bipolar disorder I/II (symptomatic or asymptomatic in any phase of the illness); (c) ability to provide written and informed consent; (d) obesity 30 kg/m^2; (e ) weight under 440lbs; (f) shoulder-to-shoulder width under 60 cm; Exclusion criteria are as follows: (a) age below 18 or above 65; (b) use of benzodiazepines or consumption of alcohol within 12 hours of assessments; (c) abuse of marijuana; (d) physical,

cognitive, or language impairments sufficient to adversely affect data derived from assessments; (e) diagnosed reading disability or dyslexia; (f) clinically significant learning disorder by history; (g) history of moderate or severe traumatic brain injury; (h) other neurological disorders, or unstable systemic medical diseases; and (i) pregnancy and post-partum period (j) presence of any contra-indications for MRI; (k) weight above 440lbs; (l) shoulder-to-shoulder width greater than 60 cm. All subjects will be consented prior to initiating the study; (m) >45 BMI; (n) suicidality as determined by clinical discretion.

### Measurements Obtained at Single Visit

#### 1. Sociodemographic:

- a. Age
- b. Sex
- c. Education
- d. Employment Status
- e. Education Attainment
- f. Marital Status
- g. Ethnicity and Race

#### 2. Illness Measurements:

- a. Severity of depression will be assessed with the Quick Inventory of Depressive Symptomatology (QUIDS)
- b. Measurement of anhedonia composite (SHAPS)
- c. Self-rated cognitive measurement (PDQ-5) Perceived Deficit Questionnaire 5
- d. Objective cognitive measurement (TMTA/B)
- e. Digit Symbol Substitution Test (DSST)
- f. UCLA Loneliness Scale

- g. Food Diary
  - h. Calorimetry
  - i. Anxiety Measurement (Hamilton Anxiety Scale) (HAMD)
  - j. Age of onset
  - k. Number of episodes
  - l. Number of hospitalizations
  - m. Duration of current episode
  - n. Psychiatric comorbidity
  - o. Number of treatments
3. Medical Assessment:
- a. Weight
  - b. Height
  - c. Waist circumference
4. Laboratory Measures:
- a. Blood glucose
  - b. Cholesterol and fractionation (E.g. HDL, LDL and triglycerides)
  - c. Insulin levels
  - d. Interleukin 1, interleukin 6, interleukin 10, tumor necrosis factor alpha, c reactive peptide, adiponectin, leptin, ghrelin, DPP-IV
  - e. Oxidative stress markers (e.g. TBARS)
5. Effort Expenditure for Rewards Task (EEfRT)
6. Monetary Incentive Delay (MID) task
7. Probabilistic Reward Task (PRT)
8. MRI Scan

All assessments and scan will be done on the same day.

## Procedures for Participants

### **Visit 1**

The single visit entails the provision of detailed study information to participant and obtainment of informed written consent, as well as completion of all questionnaires, activities, MRI, and participant compensation. The psychiatrists will assess participants' eligibility based on inclusion/exclusion criteria and confirm a diagnosis of MDD or BD based on their scheduled appointment visit. Demographics including date of birth, sex, and race will be recorded. Years of education will be recorded as well. Psychiatric and medical history, number of psychotropic medications received according to participant self-report/clinical chart review, as well as anthropometrics (including height, weight and waist circumference) will be measured. Participants will complete a series of questionnaires to assess their illness. These include: Quick Inventory of Depressive Symptomatology (QIDS), Snaith-Hamilton Pleasure Scale (SHAPS), Perceived Deficits Questionnaire for Depression (PDQ-5-D), Hamilton Depression Rating Scale (HAMD). Participants will also have loneliness assessed by participating in the UCLA Loneliness Scale. All self-reports will be administered by a member of the study team. Participants will record their food intake via a Food Diary, and will have a Calorimetry test taken. Participants will also complete cognitive measures including the Trail Making Test A/B (TMT A/B), and the Digit Symbol Substitution Test (DSST). Participants will then complete the Monetary Incentive Delay (MID) task, as well as the Probabilistic Reward Task (PRT). All study procedures will take place in a quiet setting. Fasting (12-hours) clinical and research bloodwork will also be collected. Participants will be escorted by a study member to the MRI facility where they will complete the MRI and the Effort Expenditure for Rewards Task (EEfRT). Upon completion of the MRI, participants will receive the reimbursement fee for their participation in the study.

### **Adverse Events**

#### Definitions:

Adverse event: An adverse event is the development of an undesirable medical condition or the deterioration of a pre-existing medical condition following or during exposure to a pharmaceutical product, whether or not considered causally related to the product. An

undesirable medical condition can be symptoms (e.g., nausea, chest pain), signs (e.g., tachycardia, enlarged liver) or the abnormal results of an investigation (e.g., laboratory findings, electrocardiogram). In clinical studies, an AE can include an undesirable medical condition occurring at any time, including run-in or washout periods, even if no study treatment has been administered.

Serious adverse event: A serious adverse event is an AE occurring during any study phase (i.e., run-in, treatment, washout, follow-up), and at any dose of the investigational product, comparator or placebo, that fulfils one or more of the following criteria:

- results in death
- is immediately life-threatening
- requires in-patient hospitalization or prolongation of existing hospitalization
- results in persistent or significant disability or incapacity
- is a congenital abnormality or birth defect
- is an important medical event that may jeopardize the patient or may require medical intervention to prevent one of the outcomes listed above.

The causality of SAEs (i.e., their relationship to study treatment) will be assessed by the investigator(s). Note that SAEs that could be associated with any study procedure should also be reported. For such events the casual relationship is implied as "yes".

#### Recording of Adverse Events

AEs will be collected during each visit. At each visit, subjects will be asked if they have had any health problems since the previous visit. All AEs will be recorded appropriately, whether or not considered related to the investigational product. This will include AEs spontaneously reported by the patient and/or observed by the staff as well as AEs reported in response to a direct question e.g. "Have you had any health problems since your last visit?"

For each AE, the following parameters be described:

- start and stop date
- action taken with regards to investigational product
- outcome
- if the AE caused the patient to discontinue
- a statement if the AE fulfils the criteria for a SAE or not

- the investigator's assessment of the causal relationship between the event and the investigational product
  - intensity of the AE
    - o mild (awareness of sign or symptom, but easily tolerated)
    - o moderate (discomfort sufficient to cause interference with normal activities)
    - o severe (incapacitating, with inability to perform normal activities)

It is important to distinguish between serious and severe AEs. Severity is a measure of intensity whereas seriousness is defined by the criteria in Section. An AE of severe intensity need not necessarily be considered serious. For example, nausea that persists for several hours may be considered severe nausea, but not an SAE. On the other hand, a stroke that results in only a limited degree of disability may be considered a mild stroke but would be an SAE.

Symptoms associated with overdose should be reported as AEs. For further information regarding overdose, see section.

Pregnancy in itself is not regarded as an AE unless there is a suspicion that an investigational product may have interfered with the effectiveness of a contraceptive medication.

Follow-up of adverse events should be based upon the clinical judgement of the investigator.

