#### Reporting of Serious Adverse Events

Reporting of SAEs to regulatory authorities will be done by the investigator in accordance with local regulations. A copy of the report will also be sent to the manufacturer of the investigational product.

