#### **Risks Related to Being in the Study**

This study has risks. Some of these risks we know about. There is also a possibility of risks that we do not know about that have not been seen in study participants to date. Some can be managed. Please call the study doctor if you have any side effects even if you do not think they have anything to do with this study. The risks we know of are:

- a) MRI risks: There are few potential risks of having an MRI scan, as it is a non-invasive procedure and does not involve any radiation. The main potential risk comes from loose metal objects, which, if taken near the scanner, could be dangerous. The combination of the noise of the scanner and confined space can also be stressful for people who feel uncomfortable in closed spaces.

- b) Blood draw risks: Drawing blood may cause very mild pain, bruising, redness, and rarely infection at the needle stick.
- c) Other risks: In addition to medical risks, being in this study may make you feel uncomfortable. You will be asked personal questions about your psychiatric and medical history. You may refuse to answer questions or stop the interview at any time if there is any discomfort. Administering the cognitive testing may sometimes be frustrating particularly if you are not performing as well as you think you should, and may also lead to mild mental and physical fatigue.

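### The adverse-event rules are written for a multi-visit drug trial and do not fit a one-day study with no described product, so non-serious procedure-related events are weakly elicited and cannot be attributed

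*Combined protocol and SAP*

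**What the plan says.** The protocol sets out a study completed in one day. Under Visit 1, "The single visit entails the provision of detailed study information to participant", and the same paragraph covers consent, all assessments, blood sampling, the scan and payment. The measurement list closes with "All assessments and scan will be done on the same day". The last step described for a participant is "Upon completion of the MRI, participants will receive the reimbursement fee for their participation in the study". No product, comparator or placebo appears among the procedures.

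The adverse-event sections assume a different kind of study:

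- Definitions: an adverse event is a condition arising "following or during exposure to a pharmaceutical product". A serious event is framed by the dose of an investigational product, comparator or placebo.
- Recording of Adverse Events: "At each visit, subjects will be asked if they have had any health problems since the previous visit". For each event the record includes the action taken with the product and the "causal relationship between the event and the investigational product". There is also text on overdose and on interference with contraception.
- Reporting of Serious Adverse Events: "A copy of the report will also be sent to the manufacturer of the investigational product".

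The risks section lists only risks of procedures: the MRI, the blood draw ("Drawing blood may cause very mild pain, bruising, redness, and rarely infection at the needle stick"), and the discomfort, frustration and fatigue of interviews and testing.

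**The concern.** The risks that the protocol names come from its procedures, while its recording rules are organised around a product and a sequence of visits. Three practical gaps follow. The scripted question has nothing to look back to. Nothing places a safety question after the scan and blood draw, when procedure-related complaints would have arisen. The causality item offers no way to say that an event was due to the needle, the scanner or the testing.

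At stake is the quality of the safety record. Where non-serious events depend on participants volunteering them or staff noticing them, few reports cannot be read as few events. The participants are adults with obesity and a mood disorder in any phase, symptomatic phases included. They undergo a 12-hour fast, venepuncture, personal questions, cognitive testing and a confined, noisy scan. A simple, reliable record of how they tolerated the day is a reasonable expectation.

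**Working it through.** The protocol gives no figure to reproduce here, and the point involves no power, error rate or effect size. The check is a count of contacts followed by a comparison of sections.

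**Contacts.** Planned study visits: 1 (Visit 1; Synopsis). Earlier study visits for the scripted question to refer to: 1 − 1 = 0. Planned contacts after the participant leaves: 0, since Visit 1 ends with the MRI and payment. This is the same for all 20 planned participants.

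**Could another visit serve as the reference?** Visit 1 mentions a scheduled appointment at which the psychiatrist confirms the diagnosis. Its relation to the study visit is unclear. Even if it counted as the earlier visit, the recording section does not say when during the study day the question is asked. Asked early in the day, it would precede the blood draw and scan and could not pick up their effects.

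**Items recorded per event.** The recording section lists seven: dates, action taken with the product, outcome, whether the event led to discontinuation, seriousness, causality and intensity. Two of the seven (action and causality) refer only to a product and cannot be completed meaningfully. The other five work for any event.

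**Routes into the record, by type of event:**

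| Event | Actively asked about after the procedures? | Recordable? | Attributable to a procedure? |
|---|---|---|---|
| Serious, procedure-related | Not specified | Yes, expressly reportable | Yes, relationship taken as given |
| Non-serious, during the visit (needle pain, scanner distress, fatigue) | Not specified | Yes, if volunteered or observed | No category |
| Non-serious, after leaving (for example later bruising) | No | Through a participant's call to the study doctor, though the recording section does not mention it | No category |

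The clause on study procedures in Definitions is limited to serious events. Most risks named in the risks section would ordinarily be non-serious, so that clause does not reach the events most likely to occur.

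**Text with no referent.** The product-action item, the overdose and contraception passages and the copy to a manufacturer all need a product that the protocol does not describe.

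**A related inconsistency.** The risks section opens by saying that the study carries risks. Participant Protection says that participants will be placed at none. These statements must be reconciled.

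**The case against.** The best defence is that the protocol is wider than its drug-trial wording suggests, and most of that defence stands. Definitions goes on to allow that an adverse event may occur at any time and without any study treatment, so exposure to a product is not strictly required. The recording section requires all adverse events to be recorded regardless of relation to the product, including those volunteered or seen by staff. A staff member escorts participants to the scanner, and the study team administers the questionnaires, so some complaints would arise with staff nearby. The risks section tells participants to call the study doctor about any side effect, whether or not they think it is related. The look-back wording of the question is offered as an example, and an end-of-visit question is unspecified but not ruled out.

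A reader might therefore go too far and infer that procedure-related events are not captured at all, that the safety record would be empty, that later events have no way in, or that the recall window has zero length. The documents support none of these. Volunteered, observed and serious procedure-related events are covered, a participant-initiated route exists, and a window with no starting visit is undefined, not zero.

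The defence leaves three things unanswered: no question is placed after the procedures, no post-visit contact is planned, and non-serious events have no procedure-based causality category. The call to the study doctor depends on the participant's initiative, and the recording section, which describes collection at visits, does not link to it.

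**Conclusion.** The point holds in limited form. The adverse-event text is a multi-visit drug-trial template that was not adapted to this design. As written, active elicitation of non-serious procedure-related events is inadequate, and such events cannot be attributed to the procedure that caused them.

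The severity is minor. The mismatch affects every participant, but its effect is confined to safety recording. A reader might infer that it undermines the study's results or leaves a stated tolerability aim unmet. The documents do not support that: the aims and outcomes concern obesity, reward-task performance and brain connectivity, and no adverse-event endpoint is analysed.

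The conclusion assumes that no product is given, as the procedures indicate, and that no separate procedure manual or case report form already supplies an end-of-visit question or a procedure-based causality field. If one does, the protocol should say so.

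**What to change.** Amend the adverse-event sections as follows:

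- Define an adverse event as an unfavourable event during or after a study procedure (fasting, blood draw, testing, calorimetry, MRI), and reword the serious-event definition to match.
- Ask the adverse-event question at the end of the visit, after both blood draw and MRI and before the participant leaves.
- Replace the product with the study procedure in the causality item, and have staff name the procedure concerned.
- State in Recording of Adverse Events that later calls to the study doctor, as invited in the risks section, are recorded as adverse events.
- Remove the product-action item, the overdose and product-related contraception text, and the copy to a manufacturer.
- Reconcile the statements on risk in the risks section and in Participant Protection.

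The cost is protocol wording and one end-of-visit question. No extra visit, staff or change to the analysis is needed.

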#### Reporting of Serious Adverse Events

Reporting of SAEs to regulatory authorities will be done by the investigator in accordance with local regulations. A copy of the report will also be sent to the manufacturer of the investigational product.

